#### 6.1.3. Subgroup Analysis of the Key Efficacy Endpoint

The point estimates of SVR12 rate and 2-sided 95% exact CIs based on Clopper-Pearson method {Clopper 1934} will be provided for each age group by HCV genotype (1 [further broken down to 1a and 1b], 2, 3, 4, 5, 6, or other, as appropriate, and total) within each subgroup specified in Section 3.4

A Forest plot will graphically present estimates and 95% confidence intervals of SVR12 rates for each subgroup.

### 6.2. Secondary Efficacy Endpoints

#### 6.2.1. Definition of Secondary Efficacy Endpoints

Secondary efficacy endpoints of the PK Lead-in Phase include the following:

- HCV RNA (log10 IU/mL) and change from baseline in HCV RNA (log10 IU/mL) to Day 7

Secondary efficacy endpoints of the Treatment Phase include the following:

- The percentage of subjects who attain SVR at 4 and 24 weeks after stopping therapy, defined as HCV RNA < LLOQ (ie, < 15 IU/mL) 4 and 24 weeks after stopping treatment (SVR 4 and SVR 24)
- The percentage of subjects with HCV RNA below LLOQ by study visit
- HCV RNA (log10 IU/mL) and change from baseline in HCV RNA (log10 IU/mL) through end of treatment (EOT)

- The percentage of subjects with virologic failure as the following:

#### **On-treatment virologic failure**

HCV RNA  $\geq$  LLOQ after having previously had HCV RNA  $<$  LLOQ, while on treatment, confirmed with 2 consecutive values (note, second confirmation value can be posttreatment), or last available on-treatment measurement with no subsequent follow-up values (ie, breakthrough)

$> 1 \log_{10}$ IU/mL increase in HCV RNA from nadir while on treatment, confirmed with 2 consecutive values (note, second confirmation value can be posttreatment), or last available on-treatment measurement with no subsequent follow-up values (ie, rebound)

HCV RNA persistently  $\geq$  LLOQ through 8 weeks of treatment (ie, nonresponse)

#### **Relapse**

HCV RNA  $\geq$  LLOQ during the posttreatment period having achieved HCV RNA  $<$  LLOQ at end of treatment, confirmed with 2 consecutive values or last available posttreatment measurement

- The proportion of subjects with ALT normalization (defined as ALT  $>$  ULN at baseline and ALT  $\leq$  ULN at each visit), presented by study visit
- Changes in subject and their parent/legal guardian reported outcomes including neuropsychiatric assessments based on the Pediatric Quality of Life (PedsQL™ SF-15) Questionnaires
- Characterization of HCV drug resistance substitutions at baseline, during, and after therapy with SOF/VEL

#### **6.2.2. Analysis Methods for Secondary Efficacy Endpoints**

For analyses of HCV RNA  $<$  LLOQ by visit while on treatment and during the posttreatment (SVR) follow-up period, subjects will be assigned a value at each visit based on the analysis visit windows specified in Section 3.7.2. Missing values will be imputed based on the categorical imputation rules described in Section 3.5.1. The 2-sided 95% exact confidence interval based on Clopper-Pearson method will be provided by HCV genotype (1 [further broken down to 1a and 1b], 2, 3, 4, 5, 6, or other, as appropriate, and total) for the percentage of subjects in each age group with HCV RNA  $<$  LLOQ at each visit. The overall category for “HCV RNA  $<$  LLOQ” will be split into the following 2 subcategories: “ $<$  LLOQ TND” for subjects with target not detected and “ $<$  LLOQ detected” for subjects with  $<$  LLOQ detected in tabular displays.

Graphs for the percentage of subjects with HCV RNA  $<$  LLOQ over time during treatment will be displayed by HCV genotype (1 [further broken down to 1a and 1b], 2, 3, 4, 5, 6, or other, as appropriate, and total).

Summary statistics for each age group will be presented for absolute values and change from baseline in HCV RNA ( $\log_{10}$  IU/mL) to Day 7 for PK Lead-in Phase and will be presented by HCV genotype (1 [further broken down to 1a and 1b], 2, 3, 4, 5, 6, or other, as appropriate, and total) by visit through EOT for Treatment Phase. Imputation rules described in Section 3.5.1 will be used to assign HCV RNA values for missing values at a visit that are bracketed by “< LLOQ TND” and/or “< LLOQ detected”. Otherwise, a missing excluded analysis will be performed. Plots of the mean  $\pm$  SD and median (Q1, Q3) of absolute values and changes from baseline in HCV RNA to Day 7 will be presented for PK Lead-in Phase. Plots of the mean  $\pm$  SD and median (Q1, Q3) of absolute values and changes from baseline in HCV RNA through EOT will be presented by HCV genotype (1 [further broken down to 1a and 1b], 2, 3, 4, 5, 6, or other, as appropriate, and total) for Treatment Phase.

For the SVR12 endpoint analysis, a summary table of the number and percentage of subjects with SVR12, virologic failure (VF), and Other will be created for each age group by HCV genotype (1 [further broken down to 1a and 1b], 2, 3, 4, 5, 6, or other, as appropriate, and total). All subjects who achieve SVR12 will be categorized as SVR12. Virologic failure will be descriptively summarized as “on-treatment virologic failure” and relapse (which will be broken down by study drug completed yes/no). Subjects who do not achieve SVR12 and do not meet criteria for VF will be categorized as Other. The denominator for relapse will be the number of subjects who had HCV RNA < LLOQ on their last observed on-treatment HCV RNA measurement; otherwise, the denominator will be the number of subjects in the FAS.

A concordance table between SVR12 and SVR24 will be provided. Subjects with both observed SVR12 and observed SVR24 data will be included for this analysis.

In addition, a summary table of the number and percentage of subjects with HCV RNA < LLOQ and  $\geq$  LLOQ at the posttreatment follow-up visit (observed and imputed, with reasons for imputed) will be provided by HCV genotype (1 [further broken down to 1a and 1b], 2, 3, 4, 5, 6, or other, as appropriate, and total) for each posttreatment follow-up visit. 95% Clopper-Pearson exact CIs will be presented for the overall proportion of subjects with HCV RNA < LLOQ.

Tables for ALT normalization by visit will use similar methodology to the analyses of HCV RNA < LLOQ, but will use a missing excluded analysis. Only those subjects with ALT greater than the ULN range at baseline (defined as the last ALT value collected prior to first dose of study drug) will be included in the analysis of ALT normalization.

The Pediatric Quality of Life (PedsQL™ SF 15) Questionnaires will be completed by all subjects and their parent/legal guardian up to 24-Week Posttreatment visits. The transformed scale scores (0 to 100 scale) at baseline, EOT, or at Early Termination, if applicable, 12-Week Post-Treatment, and 24-Week Post-Treatment visits and change from baseline, change from EOT to posttreatment will be presented for each of the 4 domains of the SF-15 (physical functioning, emotional functioning, social functioning, and school functioning), the psychosocial health summary (emotional, social, and school functioning domains), and the Total Score. Neuropsychiatric assessment will be based on the psychosocial health summary and domains. Scoring of the SF15 scales will be performed as described in Scaling and Scoring of the Pediatric Quality of Life Inventory™ (PedsQL™) by James W. Varni. A Wilcoxon signed rank test will

be used to explore changes in status from baseline to EOT, or at Early Termination, if applicable, and from EOT to each of the posttreatment time points. Results (p values) will be presented but should be interpreted with caution as multiple endpoints are being tested, and the study has not been powered to test these endpoints. Plot of the mean  $\pm$  SD of change from baseline in SF15 summary scores will be presented.

Drug resistant substitutions will be analyzed as part of the Virology Study Report.

### 6.3. Exploratory Efficacy Endpoints

**CCI**

[REDACTED]

[REDACTED]

[REDACTED]

[REDACTED]

[REDACTED]

[REDACTED]

[REDACTED]

[REDACTED]

[REDACTED]

[REDACTED]

### 6.4. Changes From Protocol-Specified Efficacy Analyses

There are no changes from protocol-specified efficacy analyses.

## **7. SAFETY ANALYSES**

### **7.1. Adverse Events and Deaths**

#### **7.1.1. Adverse Event Dictionary**

Clinical and laboratory adverse events (AEs) will be coded using Medical Dictionary for Regulatory Activities (MedDRA). System organ class (SOC), high-level group term (HLGT), high-level term (HLT), preferred term (PT), and lower-level term (LLT) will be provided in the AE dataset.

#### **7.1.2. Adverse Event Severity**

Adverse events are graded by the investigator as Grade 1, 2, 3, or 4 according to toxicity criteria specified in the protocol. The severity grade of events for which the investigator did not record severity will be categorized as “missing” for tabular summaries and data listings and the most severe will be considered (for sorting purpose only) in data presentation.

#### **7.1.3. Relationship of Adverse Events to Study Drug**

Related AEs are those for which the investigator selected “Related” on the AE eCRF to the question of “Related to Study Treatment”. Events for which the investigator did not record relationships to study drug will be considered related to study drug for summary purposes. However, by-subject data listings will show the relationship as missing from that captured on the CRF.

#### **7.1.4. Serious Adverse Events**

Serious adverse events (SAEs) will be identified and captured as SAEs if AEs met the definitions of SAE specified in the study protocol. Serious adverse events captured and stored in the clinical database will be reconciled with the SAE database from the Gilead Pharmacovigilance and Epidemiology Department before database finalization.

#### **7.1.5. Treatment-Emergent Adverse Events**

##### **7.1.5.1. Definition of Treatment Emergent**

Treatment-emergent adverse events (TEAEs) are defined as one or both of the following:

- Any AEs with an onset date on or after the study drug start date and no later than 30 days after permanent discontinuation of study drug.
- Any AEs leading to premature discontinuation of study drug.

#### 7.1.5.2. Incomplete Dates

If the onset date of the AE is incomplete, then the month and year (or year alone if month is not recorded) of onset determine whether an AE is treatment emergent, as long as the AE stop date is not prior to the first dose date of study drug. The event is considered treatment emergent if both of the following 2 criteria are met:

- The AE onset and end dates are the same as or after the month and year (or year) of the first dose date of study drug
- The AE onset date is the same as or before the month and year (or year) of the 30th day after the date of the last dose of study drug

An AE with completely missing onset and stop dates, or with the onset date missing and a stop date later than the first dose date of study drug, will be considered to be treatment emergent.

#### 7.1.6. Summaries of Adverse Events and Deaths

A brief high-level summary of TEAEs will be provided for each age group by presenting the number and percentage of subjects who had the following: any AE; any AE of Grade 3 or above; any AE of Grade 2 or above; any treatment-related AE; any treatment-related AE of Grade 3 or above; any treatment-related AE of Grade 2 or above; any SAE; any treatment-related SAE; any AE that led to premature discontinuation of SOF/VEL; any AE that led to interruption of SOF/VEL. All deaths (including those that are treatment emergent and those that are not treatment emergent) observed during the study will also be summarized and included in this table.

Adverse event summaries will provide the number and percentage of subjects with TEAEs by SOC and PT in each age group, based on the Safety Analysis Set as follows:

- All AEs
- AEs of Grade 3 or above
- AEs of Grade 2 or above
- All treatment-related AEs
- Treatment-related AEs of Grade 3 or above
- Treatment-related AEs of Grade 2 or above
- All SAEs
- All treatment-related SAEs
- AEs leading to premature discontinuation of SOF/VEL
- AEs leading to interruption of SOF/VEL

Multiple events will be counted only once per subject in each summary. Adverse events will be summarized and listed first in alphabetic order of SOC and then by PT in order of descending incidence overall within each SOC. In summaries by severity grade, the most severe grade will be used for those AEs that occurred more than once in an individual subject during the study.

In addition to the above summary tables, TEAEs will be summarized by PT only, in order of descending incidence for:

- AEs that occurred in at least 5% of subjects within any age group
- AEs of Grade 3 or above
- All treatment-related AEs
- All SAEs
- AEs leading to premature discontinuation of SOF/VEL
- AEs leading to interruption of SOF/VEL

In addition to the summaries described above, data listings will be provided for the following:

- All AEs (with a variable indicating whether the event is treatment emergent)
- AEs of Grade 3 or above
- SAEs
- Deaths
- AEs leading to premature discontinuation of SOF/VEL
- AEs leading to interruption of SOF/VEL

## **7.2. Laboratory Evaluations**

Laboratory data collected during the study will be analyzed and summarized using both quantitative and qualitative methods. Summaries of laboratory data will be provided for the Safety Analysis Set and will include data collected up to the last dose of study drug plus 30 days for subjects who have permanently discontinued study drug. The analysis will be based on values reported in conventional units. When values are below the limit of quantitation, they will be listed as such, and the closest imputed value will be used for the purpose of calculating summary statistics. For example, if “< 0.2” was recorded, a value of 0.1 will be used for the purpose of calculating summary statistics; if “< 0.1” was recorded, a value of 0.09 will be used for the purpose of calculating summary statistics.

A by-subject listing for laboratory test results will be provided by subject ID number and visit in chronological order for hematology, serum chemistry, and urinalysis separately. Values falling outside of the relevant reference range and/or having a severity grade of 1 or higher on the Gilead Grading Scale for Severity of Adverse Events and Laboratory Abnormalities will be flagged in the data listings, as appropriate.

No inferential statistics will be generated.

### **7.2.1. Summaries of Numeric Laboratory Results**

Descriptive statistics (n, mean, SD, median, Q1, Q3, minimum, and maximum) will be provided by age group for ALT, aspartate aminotransferase (AST), total bilirubin, alkaline phosphatase, hemoglobin, reticulocytes, white blood cell (WBC), neutrophils, lymphocytes, platelets, and international normalized ratio (INR) as follows:

- Baseline values
- Values at each postbaseline analysis window
- Change from baseline at each postbaseline analysis window

A baseline laboratory value will be defined as the final assessment performed on or prior to the date/time of first dose of study drug. Change from baseline to a postbaseline visit will be defined as the visit value minus the baseline value. The mean, median, Q1, Q3, minimum, and maximum will be displayed to the reported number of digits; SD to the reported number of digits plus 1.

Median (Q1, Q3) of the observed values for these laboratory parameters will be plotted using a line plot by visit.

In the case of multiple values in an analysis window, data will be selected for analysis as described in Section 3.7.3 (Selection of Data in the Event of Multiple Records in a Window).

The number of subjects with hemoglobin < 10 g/dL and < 8.5 g/dL at any postbaseline visits (up to 30 days after the last dose of any study drug) will be summarized.

### **7.2.2. Graded Laboratory Values**

The Gilead Grading Scale for Severity of Adverse Events and Laboratory Abnormalities will be used for assigning toxicity grades to laboratory results for analysis as Grade 0, Grade 1, Grade 2, Grade 3, or Grade 4. Grade 0 includes all values that do not meet the criteria for an abnormality of at least Grade 1. Some laboratory tests have criteria for both increased and decreased levels; analyses for each direction (ie, increased, decreased) will be presented separately.

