6.10. Procedures and Specifications

6.10.1. Clinical Laboratory Analytes

Hematology: Hematocrit, hemoglobin (Hb), platelet count, red blood cell count (RBC), white blood cell count (WBC) with differential (absolute and percentage) including lymphocytes, monocytes, neutrophils, eosinophils, basophils, reticulocyte count and mean corpuscular volume (MCV).

Coagulation: INR, Prothrombin time (PT), Activated partial thromboplastin time (APTT)

Chemistry: Alanine aminotransferase (ALT/SGPT), aspartate aminotransferase (AST/SGOT), albumin, alkaline phosphatase, creatinine, total bilirubin (reflex to direct bilirubin), glucose, lipase, potassium, sodium, gamma-glutamyl transferase (GGT) and creatine kinase (CK).

Urinalysis: Appearance, blood, color, glucose, leukocyte esterase, pH, protein, urobilinogen. Reflex to microscopic urinalysis if dipstick result is abnormal.

Virological Tests: Serologies for HCV, HBV (HBsAg, HBsAb, HBcAb) and HAV. HBV DNA testing will be performed in subjects HBcAb positive at Screening. Serology and/or antigen testing for HIV (including reflex testing as necessary). HCV RNA will be measured using the COBAS[®] AmpliPrep/COBAS[®] TaqMan[®] HCV Test, v2.0 for Use with the High Pure System. HCV GT and subtype will be determined using the Siemens VERSANT[®] HCV Genotype INNO-LiPA 2.0 Assay. Gilead reserves the right to use alternate assays for HCV RNA and HCV GT should the above assays become unavailable.

IL28B genotype will be determined by polymerase chain reaction (PCR) amplification of the SNP, rs12979860, with sequence specific forward and reverse primers and allele specific fluorescently labeled TaqMan[®] MGB probes. Gilead reserves the rights to use alternate assays for IL28B determination should the above assay become unavailable.

Pregnancy Tests: Serum β -hCG, Urine β -hCG (if positive, requires immediate confirmation with Serum β -hCG)

Additional Tests: Urine drug screen (for amphetamines, cocaine, methadone, opiates), hemoglobin A_{1c} (HbA_{1c}), TSH (reflex Free T₄), alpha-1 anti-trypsin (AAT), Fibrotest, and APRI.

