8.5.3. Laboratory Evaluations

Selected laboratory data (using conventional units) will be summarized (n, mean, SD, median, Q1, Q3, minimum, and maximum) by study visit along with the corresponding change from baseline.

Graded laboratory abnormalities will be defined using the laboratory toxicity grading scheme defined in [Appendix 3](#).

Incidence of treatment-emergent laboratory abnormalities, defined as values that increase by at least one toxicity grade from baseline at any time post baseline up to and including the date of last dose of study drug plus 30 days, will be summarized.

Values for missing safety laboratory data will not be imputed; however, a missing Day 1 result will be replaced with a screening result, if available. If no pretreatment laboratory value is available, the baseline value will be assumed to be normal (i.e., no grade [Grade 0]) for the summary of graded laboratory abnormalities.

All laboratory abnormalities will be included in the listings of laboratory data.

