Appendix 3. GSI Grading Scale for Severity of Adverse Events and Laboratory Abnormalities

Antiviral Toxicity Grading Scale Version: 01 April 2015

HEMATOLOGY				
	Grade 1	Grade 2	Grade 3	Grade 4
Hemoglobin HIV POSITIVE Adult and Pediatric ≥ 57 Days	8.5 to 10.0 g/dL 85 to 100 g/L	7.5 to < 8.5 g/dL 75 to < 85 g/L	6.5 to < 7.5 g/dL 65 to < 75 g/L	< 6.5 g/dL < 65 g/L
HIV NEGATIVE Adult and Pediatric ≥ 57 Days	10.0 to 10.9 g/dL 100 to 109 g/L OR Any decrease from Baseline 2.5 to < 3.5 g/dL 25 to < 35 g/L	9.0 to < 10.0 g/dL 90 to < 100 g/L OR Any decrease from Baseline 3.5 to < 4.5 g/dL 35 to < 45 g/L	7.0 to < 9.0 g/dL 70 to < 90 g/L OR Any decrease from Baseline ≥ 4.5 g/dL ≥ 45 g/L	< 7.0 g/dL < 70 g/L
Infant, 36–56 Days (HIV POSITIVE OR NEGATIVE)	8.5 to 9.4 g/dL 85 to 94 g/L	7.0 to < 8.5 g/dL 70 to < 85 g/L	6.0 to < 7.0 g/dL 60 to < 70 g/L	< 6.0 g/dL < 60 g/L
Infant, 22–35 Days (HIV POSITIVE OR NEGATIVE)	9.5 to 10.5 g/dL 95 to 105 g/L	8.0 to < 9.5 g/dL 80 to < 95 g/L	7.0 to < 8.0 g/dL 70 to < 80 g/L	< 7.0 g/dL < 70 g/L
Infant, 1–21 Days (HIV POSITIVE OR NEGATIVE)	12.0 to 13.0 g/dL 120 to 130 g/L	10.0 to < 12.0 g/dL 100 to < 120 g/L	9.0 to < 10.0 g/dL 90 to < 100 g/L	< 9.0 g/dL < 90 g/L
Absolute Neutrophil Count (ANC) Adult and Pediatric, ≥ 7 Months[#]	1000 to 1300/mm ³ 1.00 to 1.30 GI/L	750 to < 1000/mm ³ 0.75 to < 1.00 GI/L	500 to < 750/mm ³ 0.50 to < 0.75 GI/L	< 500/mm ³ < 0.50 GI/L
Absolute CD4+ Count HIV NEGATIVE ONLY Adult and Pediatric > 13 Years	300 to 400/mm ³ 300 to 400/μL	200 to < 300/mm ³ 200 to < 300/μL	100 to < 200/mm ³ 100 to < 200/μL	< 100/mm ³ < 100/μL

HEMATOLOGY				
	Grade 1	Grade 2	Grade 3	Grade 4
Absolute Lymphocyte Count HIV NEGATIVE ONLY Adult and Pediatric > 13 Years	600 to 650/mm ³ 0.60 to 0.65 GI/L	500 to < 600/mm ³ 0.50 to < 0.60 GI/L	350 to < 500/mm ³ 0.35 to < 0.50 GI/L	< 350/mm ³ < 0.35 GI/L
Platelets	100,000 to < 125,000/mm ³ 100 to < 125 GI/L	50,000 to < 100,000/mm ³ 50 to < 100 GI/L	25,000 to < 50,000/mm ³ 25 to < 50 GI/L	< 25,000/mm ³ < 25 GI/L
WBCs	2000/mm ³ to 2500/mm ³ 2.00 GI/L to 2.50 GI/L	1,500 to < 2,000/mm ³ 1.50 to < 2.00 GI/L	1000 to < 1,500/mm ³ 1.00 to < 1.50 GI/L	< 1000/mm ³ < 1.00 GI/L
Hypofibrinogenemia	100 to 200 mg/dL 1.00 to 2.00 g/L	75 to < 100 mg/dL 0.75 to < 1.00 g/L	50 to < 75 mg/dL 0.50 to < 0.75 g/L	< 50 mg/dL < 0.50 g/L
Hyperfibrinogenemia	> ULN to 600 mg/dL > ULN to 6.0 g/L	> 600 mg/dL > 6.0 g/L	— —	— —

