#### 7.2.2.1. Treatment-Emergent Laboratory Abnormalities

Treatment-emergent laboratory abnormalities are defined as values that increase at least 1 toxicity grade from baseline at any postbaseline time point, up to and including the date of last dose of study drug plus 30 days for subjects who permanently discontinued study drug. If the relevant baseline laboratory value is missing, then any abnormality of at least Grade 1 will be considered treatment emergent.

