#### 7.2.2.2. Summaries of Laboratory Abnormalities

Laboratory data that are categorical will be summarized using the number and percentage of subjects in the study with the given response at baseline and each scheduled postbaseline visit.

The following summaries (number and percentage of subjects) for treatment-emergent laboratory abnormalities will be provided by analyte in each age group; subjects will be categorized according to the most severe postbaseline abnormality grade for a given analyte:

- Graded laboratory abnormalities
- Grade 3 or above laboratory abnormalities

For all summaries of laboratory abnormalities, the denominator is the number of subjects with nonmissing postbaseline values up to 30 days after last dose for the laboratory parameter of interest.

A by-subject listing of treatment-emergent Grade 3 or above laboratory abnormalities will be provided by subject ID number and visit in chronological order. This listing will include all test results that were collected throughout the study for the analyte of interest, with all applicable severity grades or abnormal flags displayed.

For subjects with at least one event of treatment-emergent Grade 3 or above laboratory abnormality of creatine kinase (CK) or lipase, a listing of AEs will be provided.

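### Lymphocytes have grading criteria only above age 13, so the graded laboratory tables, followed as written, show 0/n for both age groups under 12 whatever the data

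*SAP*

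**What the plan says.** - **Which scale.** Protocol 8.5.3: "Graded laboratory abnormalities will be defined using the laboratory toxicity grading scheme defined in" Appendix 3. SAP 7.2.2 agrees that the sponsor's scale "will be used for assigning toxicity grades to laboratory results for analysis as Grade 0, Grade 1, Grade 2, Grade 3, or Grade 4".
- **What the scale covers.** The only lymphocyte row in Appendix 3 is headed "Absolute Lymphocyte Count HIV NEGATIVE ONLY Adult and Pediatric > 13 Years". No row covers age 13 or younger. HIV co-infection is an exclusion criterion (Protocol 4.3), so this row is the relevant one.
- **What is measured.** Protocol 6.10.1 puts lymphocytes in the hematology panel for all subjects: "white blood cell count (WBC) with differential (absolute and percentage) including lymphocytes". Protocol Appendix 2 schedules hematology at Day 1, Week 1 (Day 7 in the PK Lead-in), Weeks 4, 8 and 12, early termination and posttreatment Week 4.
- **Grade 0.** SAP 7.2.2: "Grade 0 includes all values that do not meet the criteria for an abnormality of at least Grade 1".
- **Treatment-emergent.** SAP 7.2.2.1: "values that increase at least 1 toxicity grade from baseline at any postbaseline time point". If baseline is missing, any postbaseline grade of 1 or more counts.
- **Tables.** SAP 7.2.2.2: summaries "for treatment-emergent laboratory abnormalities will be provided by analyte in each age group", and "the denominator is the number of subjects with nonmissing postbaseline values up to 30 days after last dose for the laboratory parameter of interest".

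Neither document has a category for values that cannot be graded, or another lymphocyte criterion for younger children.

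**The concern.** The trial enrolls ages 3 to <18, but the lymphocyte criteria start above 13. The Grade 0 rule is a residual: whatever fails to reach Grade 1 falls into it. The denominator asks only that a result exists, not that it can be graded. Together these rules make a child with no applicable criteria look the same as a child who was assessed and found normal.

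Safety and tolerability is the primary objective of the Treatment Phase, and laboratory abnormalities are tabulated by age group. A reader comparing the columns would see no lymphocyte abnormality in the two younger groups and possibly some in adolescents. That difference could come entirely from the scale.

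**Working it through.** The documents give no figure for this point, so there is none to reproduce. The check is to apply the rules as written.

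**1. Grade a value.** From Appendix 3, for age above 13 (counts per mm³): Grade 1 is 600 to 650, Grade 2 is 500 to <600, Grade 3 is 350 to <500, Grade 4 is <350. Otherwise Grade 0 under SAP 7.2.2.

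| Age (years) | 100 | 400 | 550 | 640 | 2000 |
|---|---|---|---|---|---|
| 4, 8, 11.9, 12.5, 13 | 0 | 0 | 0 | 0 | 0 |
| 14 | 4 | 3 | 2 | 1 | 0 |

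**2. Apply the treatment-emergent rule.** With every value at Grade 0, a rise of one grade is impossible. The missing-baseline rule does not help, because it also needs a postbaseline value of at least Grade 1. The numerator is therefore 0 in the 3 to <6 and 6 to <12 groups.

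**3. Apply the denominator.** Every child with a postbaseline lymphocyte result counts, so the row reads 0/n. This does not depend on how the Grade 0 sentence is programmed. If the grade were left missing, the child would still be in the denominator, because the rule asks for a value and not for a grade.

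**4. Subjects affected.** The 3 to <12 group has about 100 of 200 planned subjects (SAP 1.2). Some adolescents are affected too. The documents give no age distribution, so assume ages uniform over the six years from 12 to <18:
- criteria apply from the 13th birthday: 1/6 of adolescents lack criteria, and (100 + 100/6)/200 = 58% of the trial;
- criteria apply from the 14th birthday: 2/6 = 1/3 lack criteria, and (100 + 100/3)/200 = 67%.

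**5. Dilution in adolescents.** If a share f has no criteria, the printed rate is the rate among gradable subjects × (1 − f). For an assumed 5% rate:
- f = 1/6: 5% × 5/6 = 4.2%;
- f = 1/3: 5% × 2/3 = 3.3%.

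**6. Whether other graded analytes cover the gap.** In Appendix 3, WBC is graded at 2500/mm³ or below with no age limit, and ANC at 1300/mm³ or below from 7 months. Take WBC 4000, neutrophils 3300 and lymphocytes 300/mm³. Neither WBC nor ANC is graded. The lymphocyte count is Grade 4 at age 14 and Grade 0 at age 8.

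**The case against.** **The SAP never says that a value without criteria is Grade 0.** This is correct. Failing to meet criteria can be read as presupposing that criteria exist, and a note in Appendix 3 refers to graded tests as a class. A careful programmer might show the row as not graded. That would be an unwritten convention, though, and the denominator rule, which is explicit, gives 0/n under either reading.

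**Low counts are reported elsewhere.** This stands, and it limits the point. SAP 7.2.1 summarizes lymphocytes by age group at baseline and each postbaseline window, including the minimum and change from baseline, with a median plot. SAP 7.2 flags out-of-range results in by-subject listings whether or not they are graded. An abnormality that needs intervention or leads to interruption or discontinuation of study drug must be recorded as an adverse event (Protocol 7.1.3). What these outputs lack is a count of affected children. By-visit summaries also take the record closest to the nominal day (SAP 3.7.3), so an unscheduled low value can drop out of them.

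**Laboratory grades are not the primary endpoint.** Also correct. The Treatment Phase endpoint is adverse events, with a focus on those leading to discontinuation (Protocol 8.1.2), and nothing in the documents names lymphopenia as an expected risk.

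**A reader might infer a safety bound from the zero.** Taken at face value, 0/100 has an exact 95% upper limit of 1 − 0.025^(1/100) = 3.6%. The trial would not report this, since SAP 7.2 rules out inferential statistics for laboratory data. It shows only what an outside reader could wrongly conclude.

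**Conclusion.** The point holds for the graded laboratory outputs and no further. As written, the lymphocyte row is 0/n for both groups under 12 years, about 100 of 200 subjects, at any count. The 12 to <18 rate is diluted by subjects aged 13 or younger. No subject without criteria can enter the treatment-emergent Grade 3 or above listing through lymphocytes.

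A reader might go further and conclude that lymphopenia in young children would be invisible in this trial. The documents do not support that, because the numeric summaries and flagged listings remain.

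The zero rests on the text alone. The 58% to 67% range and the 4.2% to 3.3% illustration rest on an assumed uniform age distribution, and the illustration also on an assumed 5% rate. The change should be made because an unassessed row would otherwise read as a clean one, but it is not critical.

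**What to change.** In SAP 7.2.2.2:

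1. Restrict the numerator and denominator of each graded analyte to subjects whose age has criteria for that analyte in Appendix 3.
2. State how the age limit of 13 is applied: from the 13th or the 14th birthday, and whether at first dose (the age that SAP 3.6 uses for analyses) or at sampling.
3. Show all other subjects as not graded, not as Grade 0, and make the matching exception in SAP 7.2.2.

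This takes a few sentences and one programming condition, with no new data. The lymphocyte row for ages under 12 then carries no rate, which is accurate.

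Optionally, for subjects without lymphocyte criteria, report the number with a postbaseline value below the laboratory's age-specific LLN among those not below LLN at baseline. The baseline condition keeps the count in line with the treatment-emergent definition; without it, children already low at entry would be counted. The cost is one small extra derivation and output. The reference ranges are already used for flagging in SAP 7.2.
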